Two clinical studies were conducted on the now marketed dentifrice to evaluate the build up of extrinsic dental stain, following professional prophylaxis. In an 8 week study a marketed SnF_2 dentifrice; RDA~146 (Crest Pro-Health^{™*}) exhibited greater stain build up compared to the test SnF_2 dentifrice, and no statistically significant differences in dental stain build up were observed between the then test SnF_2 dentifrice and a standard fluoride dentifrice; RDA~80 (Colgate Cavity Protection[®]), after 8 weeks twice daily use [GSKCH study CCI [REDACTED]]. In a longer use 24 weeks study, a statistically significant difference in favour of the SnF_2 dentifrice versus the

^{™*} Crest Pro-Health is a registered trademark of Proctor and Gamble.

[®] Colgate is a registered trademark of the Colgate-Palmolive group.

Document Name	207872 Clinical Protocol.doc		
Type	Version	Document Identifier	Effective Date
elido_clinical_doc	5.0; Most-Recent; Effective; CURRENT	090032d580d488e0	30-May-2017 04:37:09
Reason For Issue	Auto Issue		

same standard fluoride dentifrice (Colgate Cavity Protection[®]) was observed after 24 weeks twice daily use [GSKCH study CCI [REDACTED]].

It is an important compromise that a dentifrice should be able to control extrinsic dental stain while minimising its abrasive effect [Schemehorn, 2011], particularly for people with tooth sensitivity where the softer dentin is exposed [Pickles, 2006].

Therefore, a lower abrasivity dentifrice is considered to be more appropriate for DH sufferers. GSKCH have therefore developed two experimental dentifrice formulations which have lower RDA values of ~52 and RDA of ~80, to support an overall lower abrasion/ enamel protection proposition.

Document Name	207872 Clinical Protocol.doc		
Type	Version	Document Identifier	Effective Date
elido_clinical_doc	5.0; Most-Recent; Effective; CURRENT	090032d580d488e0	30-May-2017 04:37:09
Reason For Issue	Auto Issue		

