3.3. Study Design and Dose Justification

This PoP single centre, randomised, examiner blind, four-treatment arm, parallel design study will be used to evaluate and compare the stain build up of two 0.454% SnF₂ / 5% STP dentifrices of differing abrasivity levels, with a marketed standard fluoride dentifrice and a marketed SnF₂ dentifrice.

• Stain will be assessed following a full professional dental prophylaxis, at intervals over a 4 week treatment period, using an established clinical measure of extrinsic dental stain - the MacPherson modification [Macpherson, 2000] of the Lobene stain index [Lobene, 1968] (MLSI). Subjects will be stratified by pre-prophylaxis MLSI

Document Name	207872 Clinical Protocol.doc		
Type	Version	Document Identifier	Effective Date
elido_clinical_doc	5.0; Most-Recent; Effective; CURRENT	090032d580d488e0	30-May-2017 04:37:09
Reason For Issue	Auto Issue		

score (total MLSI (A×I) for the facial surfaces of the 12 anterior teeth) and smoking status.

Since STP has been included in the test dentifrices to prevent SnF₂ from contributing to extrinsic dental stain, and not to directly reduce extrinsic stain caused by dietary and lifestyle habits, a stain build up design has been assessed to be the most appropriate clinical model for this study.

A 4 week treatment period has been selected for this study, as 4 weeks has been assessed to be a sufficient period of time to establish statistically significant between treatment differences for stain build up with this specific dentifrice technology. A previous 8 week study conducted by GSKCH demonstrated that although there was an increase in stain build up from Week 4 to 8, the between treatment differences observed at Week 4 were similar to those at Week 8 [GSKCH study CCI █████]. Stain assessments will also be conducted at Week 2, as this time-point was not included in earlier studies [GSKCH studies CCI █████ and CCI █████]. Therefore, it is of interest to assess the performance of the commercialised and experimental SnF₂ dentifrices at this time-point.

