Stain assessments will be made on the facial and lingual surfaces of the anterior teeth as these surfaces are considered the most aesthetically important with respect to dental stain accumulation. Dental stain largely builds up in the harder to reach interproximal areas, therefore in addition to analysis of the total MLSI (A×I) the interproximal regions have also been given focus as an exploratory objective in this study. As most of the stain is removed from the body and gingival regions, we would expect to see little change in the total gingival MLSI (A×I) and total body MLSI (A×I), therefore, these variables are not being analysed in this study. Furthermore, separate analysis of the facial and lingual surfaces are not of focus in this study. As the facial teeth are the most brushed we would expect to see little stain build up on the facial surfaces in comparison to the lingual surfaces, with little difference expected between the total MLSI (A×I) and total lingual MLSI (A×I).

A single examiner will perform the dental stain assessments for all subjects at the baseline, Week 2 and 4 visits to avoid inter-examiner variability. To assess the repeatability of the stain assessments 30 repeat examinations will be performed by the dental examiner over the duration of the study.

The dosage regimen of twice daily use (morning and evening) will be the same for all subjects, and has been selected based on widely recommended oral hygiene practice, and typical consumer habit.

Document Name	207872 Clinical Protocol.doc		
Type	Version	Document Identifier	Effective Date
elido_clinical_doc	5.0; Most-Recent; Effective; CURRENT	090032d580d488e0	30-May-2017 04:37:09
Reason For Issue	Auto Issue		

Sensodyne Complete Protection has been selected as a reference dentifrice in this study as it is a commercialised SnF₂ containing dentifrice. Colgate Cavity Protection® has been selected as a reference comparator as it is marketed globally, does not contain any ingredients known to impart extrinsic dental stain, and is considered to be representative of a moderate abrasivity standard, daily use fluoride dentifrice. Two recent stain build up studies have been conducted by GSKCH, which contain both the commercialised SnF₂ dentifrice and Colgate Cavity Protection®, providing us with a recent benchmark of relative and expected performance at the Week 4 time-point.

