9.2.4. Criteria for Assessing Efficacy

Efficacy will be evaluated based on the ranking performance of the study treatments on the stain variables. The minimum requirement will be similar, or lower levels of stain for at least one of the experimental products compared to the standard fluoride dentifrice (Colgate Cavity Protection®). The marketed SnF₂ dentifrice (Sensodyne Complete Protection) will be expected to demonstrate a comparable, or statistically significantly better performance on the stain parameters versus the experimental products and Colgate Cavity Protection®.

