3.3 Timepoints and Visit Windows

Time windows required for this study are as the following:

- Visit 2 (Baseline) is minimum 24 hours and maximum two weeks from Visit 1 (Screening)
- Visit 3 (Week 2) is 14 ± 2 Days from Visit 2
- Visit 4 (Week 4) is 28 ± 2 Days from Visit 2

4 Data Analysis

Data analysis will be performed by inVentiv Health Clinical. Prior to database closure a Blind Data Review Meeting (BDRM) will be conducted in which various aspects of the trial will be discussed and agreed. The statistical analysis software used will be SAS version 9.4.

All listings will be produced for all randomized subjects, unless otherwise stated.

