4.4 Analysis of Efficacy

4.4.1 Primary Efficacy Endpoint

4.4.1.1 Primary Efficacy Endpoint Definition

The primary endpoint is the Week 4 overall MLSI (A×I).

Each tooth site will be evaluated for stain level and will be assigned an intensity score (I) and an area score (A) by the examiner. Overall MLSI (A×I) score for each subject at each visit (Baseline, Week 2 and Week 4) is calculated as the mean MLSI (A×I) score over all gingival, body, mesial and distal sites on the facial surfaces of the six maxillary anterior teeth and six mandibular anterior teeth, and the lingual surfaces of the six mandibular anterior teeth. It is

possible that some sites could have missing values, in that case the mean is calculated over all non-missing sites

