4.4.1.2 Statistical Hypothesis, Model, and Method of Analysis

Summary statistics including mean, SD, median, min, max will be provided for baseline and Week 4 by randomised treatment group ([Table 14.2.1.1.1](#)). The overall MLSI score at Week 4 will be analysed using analysis of covariance (ANCOVA) with treatment and smoking status (smoker/non-smoker) as factor and pre-prophylaxis baseline overall MLSI score as covariate.

The primary comparisons are

- Test dentifrice (RDA-58) vs. Reference dentifrice (RDA-80)
- Test dentifrice (RDA-77) vs. Reference dentifrice (RDA-80).

All other comparisons associated with secondary and exploratory objectives will also be presented under the same analysis, namely

- Test dentifrice (RDA-58) vs. Reference dentifrice (RDA-120) (secondary)
- Test dentifrice (RDA-77) vs. Reference dentifrice (RDA-120) (secondary)
- Reference dentifrice (RDA-120) vs. Reference dentifrice (RDA-80) (secondary)
- Test dentifrice (RDA-58) vs. Test dentifrice (RDA-77) (exploratory)

Adjusted means of all treatments will be provided. Treatment differences of above mentioned comparisons will be provided together with their 95% CIs and p-values ([Table 14.2.1.1.2](#)). The assumption of residual normality in ANCOVA analysis will be investigated. If violated, data transformation or a non-parametric method (e.g., the Wilcoxon rank sum test) will be applied.

There will be no multiplicity adjustment for treatment comparisons as this study is an exploratory POP study.

Efficacy will be evaluated based on the ranking performance of the study treatments on the stain variables. The minimum requirement will be similar, or lower levels of stain for at least one of the experimental products compared to the standard fluoride dentifrice (Colgate Cavity Protection[®]). The marketed SnF₂ dentifrice (Sensodyne Complete Protection) will be expected to demonstrate a comparable, or statistically significantly better performance on the stain variables versus the experimental products and Colgate Cavity Protection[®].

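### Does the undefined word 'similar' in the minimum efficacy requirement call for a written rule before unblinding?

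*SAP*

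**What the plan says.** SAP 4.4.1.2 and protocol 9.2.4 carry almost the same paragraph. It begins "Efficacy will be evaluated based on the ranking performance of the study treatments on the stain variables". It then states "The minimum requirement will be similar, or lower levels of stain for at least one of the experimental products", compared with the standard fluoride dentifrice (RDA~80). The marketed SnF2 dentifrice (RDA~120) "will be expected to demonstrate a comparable, or statistically significantly better performance on the stain variables" against the test products and the standard fluoride product.

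No margin, confidence-limit rule, p-value rule or tolerance is attached to 'similar' or 'comparable'. On the variable that governs, SAP 4.4.1.1 says "The primary endpoint is the Week 4 overall MLSI", and 4.4.1.2 names the two test-versus-RDA~80 contrasts as primary. The same section provides adjusted means, differences, 95% CIs and p-values for all six pairwise contrasts. It declines multiplicity adjustment because the study is exploratory. Protocol 9.1 and SAP 1.4 say that the study is not powered for claims and is sized to observe trends.

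**The concern.** This is the only minimum requirement for efficacy in either document, and the text fixes its answer for some outcomes only. 'Lower' needs no definition. 'Similar' decides the result whenever both adjusted test means exceed the RDA~80 mean. Ranking cannot help there: it shows that both products rank worse, but not whether either is close enough.

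Usage elsewhere does not settle the meaning. Protocol section 1 reports an earlier comparison of the marketed SnF2 product with the same standard fluoride product as "no statistically significant differences in dental stain build up were observed between the then test" SnF2 dentifrice and that product, without calling the two similar. Protocol 3.3 uses the word loosely: "the between treatment differences observed at Week 4 were similar to those at Week 8". The sentence on the RDA~120 product sets 'comparable' against a statistically significant advantage. That hints that 'comparable' means not significantly different, but it is another word about another product.

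If the meaning is left open, the report's statement that the requirement was or was not met could be settled after the results are known.

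**Working it through.** **Inputs.** At least 220 randomised, 200 evaluable, about 50 per arm (SAP 1.4). The plan's figures agree: 200/4 = 50, 220/4 = 55, and the implied loss is 1 − 200/220 = 9.1%. No SD, expected difference, alpha or margin is stated, so everything below is in residual-SD units. The two-sided 5% level is inferred from the 95% CIs.

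**Precision.** The ANCOVA has six parameters (intercept, three treatment, one smoking, one baseline), so df = 200 − 6 = 194 and t = 1.972. The SE of a difference is sqrt(2/50) = 0.20 SD. The CI half-width is 1.972 × 0.20 = 0.394 SD (0.376 at 55 per arm).

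**The open zone.** Let D1 and D2 be the adjusted differences, test minus RDA~80, so that positive means more stain. If min(D1, D2) ≤ 0, the 'lower' limb is met. If min(D1, D2) > 0.394, both products are significantly worse. Between 0 and 0.394 the text gives no answer. The upper edge is an assumption, because no sentence sets it.

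Simulated share of trials in the zone (2,000,000 replicates per truth, both products having the same true difference):

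| True difference (SD) | Share in zone |
|---|---|
| 0.4 better | 0.4% |
| 0.2 better | 6% |
| equal | 33% |
| 0.1 worse | 53% |
| 0.2 worse | 68% |
| 0.3 worse | 71% |
| 0.5 worse | 43% |
| 0.8 worse | 4% |

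A hand check at equality: three exchangeable means put the reference lowest with probability 1/3. Both products are significantly worse in about 0.5% of trials. So 0.333 − 0.005 = 0.328, against 0.329 simulated.

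**What each reading would do.** Chance that at least one product is scored as meeting the requirement:

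| Reading of 'similar' | Equal | Both 0.3 SD worse | Both 0.5 SD worse |
|---|---|---|---|
| Counts only at or below reference | 67% | 11.5% | 1.2% |
| Difference ≤ 0.2 SD | 94% | 45% | 11.5% |
| Not significantly worse | 99.5% | 83% | 44% |
| Upper 95% limit < 0.3 SD | 47% | 4.5% | 0.3% |
| Upper 95% limit < 0.5 SD | 85% | 27% | 4.5% |

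The 0.2, 0.3 and 0.5 SD limits are illustrative. The last two rows use the normal half-width, 1.96 × 0.20 = 0.392.

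**Is one rule plainly better?**

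- *Confidence-limit margin.* For one comparison with no true difference and 80% power, n per arm = 2 × (1.96 + 0.842)² / M² = 15.70/M². That is 63 for M = 0.5 SD, 99 for 0.4 and 175 for 0.3, all above the 50 planned.
- *Non-significance.* It needs no margin, but it passes 44% of trials when both products are 0.5 SD worse.
- *Point-estimate tolerance M.* If both products are truly worse by exactly M, the reference-plus-M and the two test means are exchangeable, so at least one passes in 2/3 of trials. If M exceeds 0.394, the rule can call a significantly worse product similar. At M = 0.5 with both 0.5 SD worse, that happens in 66.7% − 44.1% = 22.6% of trials.
- *Scale and direction.* SAP 4.4.1.2 allows a transformation or a Wilcoxon test if residual normality fails, and a tolerance in MLSI units has no set meaning there. The planned contrasts run test minus RDA~120 but RDA~120 minus RDA~80, so one 'no greater than M' rule for 'comparable' would point in opposite directions.

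**What depends on the choice.** The model, adjusted means, differences, CIs and p-values in SAP Table 14.2.1.1.2 are the same under every row above.

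**The case for a change.** The best case for a change is that exploratory status excuses the lack of a confirmatory claim but does not make a stated requirement decidable. The choice of reading matters: with both products 0.3 SD worse, 'met' is reached in 11.5% of trials under the strictest point-estimate reading and in 83% under non-significance. Writing a rule would cost little. SAP section 4 offers a natural occasion ("Prior to database closure a Blind Data Review Meeting (BDRM) will be conducted"), and protocol 3.3 says two earlier studies give a "benchmark of relative and expected performance at the Week 4 time-point", which might supply a tolerance.

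Some of this stands. The words are undefined, and the readings can disagree. Two parts are weaker. The earlier studies covered the marketed SnF2 and standard fluoride products. The documents do not say that they yield a tolerable difference for the new formulations, so a tolerance would still have to be chosen on judgement. The high zone shares of 53% to 71% need both test products to be truly 0.1 to 0.3 SD worse, which no passage suggests. The other remedy, declaring the words descriptive, would alter no result, because the criterion already sits beside a ranking in an unpowered study.

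**Conclusion.** The observation is correct, but it is missing detail in a descriptive criterion and calls for no change to the plan. What is at stake is one statement in the report, namely whether the minimum requirement was met. No estimate, model, interval or p-value depends on it, and neither document attaches a claim, decision or further analysis to it. Analysts can fill the gap sensibly by reading the requirement on Week 4 overall MLSI, the stated primary endpoint. The difference and its 95% CI then stand beside whatever word is used, so a reader can see how far above the reference a product called similar might be. Any numeric rule would be a trade-off that the documents give no basis for choosing.

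The size is 33% of trials in the undefined zone if the products are truly equal and 71% if both are 0.3 SD worse. It falls to 0.4% at 0.4 SD better and 4% at 0.8 SD worse. These figures assume 50 evaluable subjects per arm, equal residual SDs, the same true difference for both products, a two-sided 5% level, and significance as the zone's upper edge. The documents do not say which true difference is likely.

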4.4.1.3 Supportive Analyses

The assumption of residual normality in ANCOVA analysis will be investigated. If violated, data transformation or a non-parametric method (e.g., the Wilcoxon rank sum test) will be applied.

4.4.2 Secondary Efficacy Variables

Secondary efficacy variable is Week 4 overall MLSI (A×I) for comparisons of

- Test dentifrice (RDA-58) vs. Reference dentifrice (RDA-120)
- Test dentifrice (RDA-77) vs. Reference dentifrice (RDA-120)
- Reference dentifrice (RDA-120) vs. Reference dentifrice (RDA-80).

These are covered under the primary efficacy section.

4.4.3 Exploratory Efficacy Variables

In addition to Week 4 overall MLSI (A×I) for the comparison between two test products (as covered in primary efficacy section), the following exploratory variables will be assessed in this study.

- Overall MLSI (A×I) score at Week 2, which will be calculated in the same way as described in Section 4.4.1.1.
- Overall interproximal MLSI (A×I) scores at Week 2 and Week 4, which will be calculated as the mean MLSI (A×I) score over all interproximal (mesial+distal) sites on the facial surfaces of the six maxillary anterior teeth and six mandibular anterior teeth, and the lingual surfaces of the six mandibular anterior teeth.
- Overall MLSI (A) scores at Week 2 and Week 4, which will be calculated as the mean MLSI (A) score over all gingival, body, mesial and distal sites on the facial surfaces of the six maxillary anterior teeth and six mandibular anterior teeth, and the lingual surfaces of the six mandibular anterior teeth.
- Overall MLSI (I) scores at Week 2 and Week 4, which will be calculated as the mean MLSI (I) score over all gingival, body, mesial and distal sites on the facial surfaces of the six maxillary anterior teeth and six mandibular anterior teeth, and the lingual surfaces of the six mandibular anterior teeth.

4.4.4 Handling of Missing Values/Censoring/Discontinuations

Missing data will not be replaced or imputed. Subjects who withdraw from the study prematurely will be included in the statistical analyses up to the point of discontinuation.

4.5 Analysis of Secondary Objectives

Secondary objectives on Week 4 overall MLSI (A×I) have been covered in primary efficacy section.

4.6 Analysis of Exploratory Objectives

Week 4 overall MLSI (A×I) for the comparison between two test products has been covered in primary efficacy section.

For Overall MLSI (AxI) at Week 2, Overall interproximal MLSI (AxI), MLSI (A) and MLSI (I) at Week 2 & 4, summary statistics (N, Mean, SD, Median, Min, Max) will be presented. These variables will also be analysed using ANCOVA with treatment and smoking status as factor and corresponding baseline overall MLSI score (interproximal, area or intensity) as covariate. Adjusted means of all treatments will be provided and treatment differences for comparisons

- Test dentifrice (RDA-58) vs. Reference dentifrice (RDA-80)
- Test dentifrice (RDA-77) vs. Reference dentifrice (RDA-80)
- Test dentifrice (RDA-58) vs. Reference dentifrice (RDA-120)
- Test dentifrice (RDA-77) vs. Reference dentifrice (RDA-120)
- Reference dentifrice (RDA-120) vs. Reference dentifrice (RDA-80)
- Test dentifrice (RDA-58) vs. Test dentifrice (RDA-77)

will be provided together with their 95% CIs and p-values. Results for overall interproximal MLSI (A×I) score, overall MLSI area score and overall MLSI intensity score will be presented in [Table 14.2.2.1](#), [14.2.2.2](#), [Table 14.2.3.1](#), [14.2.3.2](#) and [Table 14.2.4.1](#), [14.2.4.2](#) respectively.

4.7 Analysis of Safety

4.7.1 Adverse Events and Serious Adverse Events

All safety data will be reported for the Safety population as per actual treatment received. All subjects screened will be included in the list of AEs.

AE will be regarded as treatment emergent if they occur on or after the start date and time of the first treatment usage (as determined by start date and time from the EXPOSURE/dispensing panel; if this date is missing a suitable alternative will be used eg date and time of randomisation). All other AEs prior to this will be considered non-treatment emergent.

All AEs will be reviewed by Clinical Research prior to database freeze and will be coded using the Medical Dictionary for Regulatory Activities (MedDRA). During this review stage, AEs will be further categorized as oral or non-oral.

The following summary tables and listings will be presented by treatment group.

- Table of treatment emergent AEs by Oral/Non-Oral and Preferred Term ([Table 14.3.1.2](#))

- Table of treatment emergent AEs by SOC and Preferred Term ([Table 14.3.1.1](#))
- Table of treatment emergent AEs by SOC, Preferred Term and Severity ([Table 14.3.1.3](#))
- Table of Treatment emergent treatment related AEs by Oral/Non-Oral and Preferred Term ([Table 14.3.1.4](#))
- Listing of all AEs (including all subjects: Listing 16.2.7.1 for all randomised subjects; Listing 16.2.7.2 for non-randomised subjects)
- Listing of death ([Listing 14.3.2.1](#))
- Listing of non-fatal SAEs ([Listing 14.3.2.2](#))
- Listing of treatment emergent AEs leading to withdrawal ([Listing 14.3.2.3](#))
- Listing of treatment emergent AEs classified as oral ([Listing 14.3.2.4](#))

In the event that there is nothing to report a null listing will be produced.

